#### 6.11 Study closure

The study will be considered closed 30 days after the last patient has had their final follow-up visit (Visit 4).

## 7. SAFETY REPORTING

#### 7.1 Safety monitoring during the pilot study

During the pilot study, the rate of sepsis following the CPB procedure will be prospectively recorded. Between 1% and 4% of patients undergoing TRUS guided biopsy alone develop sepsis requiring hospital admission, while the sepsis rate for TPM alone is <0.5%. This is because unlike the TRUS biopsy, TPM it is not administered via the transrectal route.

Although anticipated to be rare, each sepsis case will be reviewed by the TMG and where necessary by the Trial Steering Committee (TSC). Two sepsis cases out of the 50 patients in the pilot study would represent a sepsis rate of 4%. The TSC will review safety (sepsis, urinary retention) at completion of the internal pilot study, or sooner if 2 sepsis cases requiring hospitalisation are seen (and subsequently after a 2 further cases if necessary).

If the combination of TRUS and TPM leads to more than 2 cases of sepsis at any time (requiring hospital admission), there could be cause for concern and a requirement for modification of the study design. If deemed necessary for safety reasons, recruitment to the study will be suspended either during the pilot or the main phase of the study when ongoing safety monitoring would continue.

The TSC will make a recommendation regarding proceeding to the main phase which could include a modification to the study design. For example, if a sepsis rate of 10% (n=5) is observed the study remains viable but one of the following two options could be considered: (i) introducing an interval of 6 weeks between the TRUS biopsy and the TPM (which will likely lead to increased drop-out of patients) or (ii) dropping the TRUS biopsy from the study (which will prevent an analysis of the performance of TRUS biopsy but will not compromise the primary objective of the study). The TMG would seek independent recommendation from the TSC regarding these decisions.

#### 7.2 SAE reporting

University College London is the trial sponsor and has delegated responsibility for the reporting of SAEs to the MRC CTU. In PROMIS, SAEs in the first instance should therefore be notified to the MRC CTU within one working day of becoming aware of the event, and the MRC CTU will notify UCL of all SAEs and the research ethics committees as appropriate.

Since there is no medicinal intervention in this study, there are no formal toxicity assessments. We expect adverse events to be rare in the context of this study, with the interventions being MP-MRI scanning and the CPB procedure. Potential safety issues are given in Table 3.

#### Table 3: Potential safety issues

Procedures Side effect	MP-MRI	TRUS guided biopsy	TPM biopsy
Pain/discomfort	Intravenous cannula insertion is common and causes minimal discomfort	Almost all	Pain is rare Almost all have perineal discomfort
Dysuria	Not applicable	Almost all	Almost all (self-resolving within 24 hours)
Haematuria	Not applicable	50% (self-resolving, 2-3 days)	Almost all (self-resolving, 1-3 days)
Haematospermia	Not applicable	30% (2-3 months to resolve)	Almost all (3-6 months to resolve)
Erectile dysfunction	Not applicable	About 30% (self- resolving after 6-8 weeks)	Almost all (self-resolving after 6-8 weeks)
Urinary tract infections	Not applicable	1-8%	<0.5%
Systemic urosepsis	Not applicable	1-4%	<0.5% (lower risk than TRUS - as needles do not traverse rectal mucosa)
Urinary retention	Not applicable	1%	5% (higher risk than TRUS as a result of greater gland swelling)
Symptoms associated with general/spinal anaesthetic	Not applicable	Yes	Yes
Allergic reaction to contrast medium	Yes but very rare	Not Applicable	Not Applicable

Procedure related AEs would be expected to occur within 7 days of the procedure.

Whilst there is no obligation to report a serious adverse event (SAE) to the MHRA (as there is no medicinal intervention in the study) the MRC CTU is required to report any SAE that does occur, **and which is deemed related** to **research procedures and unexpected to** the main REC. In order to meet this requirement all study sites are required to report any SAE to MRC CTU within one working day of becoming aware of the event.

The MRC CTU will report to the main REC if the SAE is an untoward and unexpected occurrence that:

- a. results in death
- b. is life-threatening
- c. requires hospitalisation or prolongation of existing hospitalisation
- d. results in persistent or significant disability or incapacity
- e. consists of a congenital anomaly or birth defect
- f. is any other important medical condition

And in the opinion of the Chief Investigator (or nominated representative) the event was:

- 'related' that is, it resulted from administration of any of the research procedures
- 'unexpected' that is, the type of event is not listed in the protocol as an expected occurrence

Centres should complete the SAE form and fax to [name]. The form will be forwarded by the MRC CTU to the Chief Investigator for assessment and reports of related and unexpected SAEs will be submitted within 7 to 15 days of the Chief Investigator becoming aware of the event to main REC.

Any queries about SAE reporting should be directed to the PROMIS Trial Manager.

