#### 6.3 Visit 4: End of study visit

The last study visit should take place within approximately one month of the CPB procedure. At this visit the clinician will discuss the results of all 3 study tests (MP-MRI, TPM biopsy and TRUS biopsy) with the patient. Any side-effects of the tests experienced by the patient can be discussed. This visit marks the end of the study for the patient. Patients will be managed according to standard care in view of the results of the study tests.

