#### 6.7 Data collection and returns

Table 2 shows the case reports forms (CRF) that are to be collected at each visit. An additional SAE form will be provided for completion as required during the study (see section 7). Please refer to PROMIS CRF completion guidelines for further details.

CRF	Screening, Consent & Registration Visit 1	MP-MRI Visit 2	CPB Visit 3	Follow-up results Visit 4
Registration	Х			
EQ-5D Questionnaire	Х	Х	Х	Х
MP-MRI Reporting Form		Х		
CPB Procedure Checklist			Х	
TPM Reporting Form			Х	
TRUS Reporting Form			Х	
End of Study				Х
SAE	Complete as required at any time following patient registration			
Withdrawal Form	Complete as required at any time following patient registration			

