The main phase of the project will provide estimates of key clinical, economic and epidemiological inputs for the model. The most important of these is likely to be the accuracy of the alternative tests (which facilitate estimates of the likelihood of falling into the diagnostic groups detailed above). However, the main phase of the project will also provide a vehicle for the collection of other relevant data to inform cost-effectiveness. These will include the costs of tests and the management of adverse events, and the health-related quality of life (HRQL) implications of any adverse events experienced with tests. The latter will be assessed using the EQ-5D instrument (see Appendix III) as part of the main clinical study. This is a widely used generic measure of HRQL which can be used to derive quality adjusted life years (QALYs). On completion of the data collection for the main phase, the evidence synthesis and modelling undertaken in the first phase will be updated, and the evidence collected in the main study added to it. Ultimately, this work will provide an assessment of the implications of any change that the use of MP-MRI has on under-detection and over-detection. These implications will be in terms of expected quality adjusted survival duration and long-term health service costs. This will allow the value for money of MP-MRI in this context to be assessed using the same metrics employed to evaluate therapeutic technologies by organisations such as NICE.

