#### Figure A1: Template Prostate Mapping Protocol

## APPENDIX III: HEALTH ECONOMICS: EQ-5D

By placing a tick in one box in each group below, please indicate which statements best describe your own health state today.

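### No EQ-5D form is scheduled in the week after the combined biopsy, so the acute quality-of-life effects it is meant to measure will largely go unrecorded

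*Protocol*

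**What the plan says.** Section 10.2.1 lists, among the data the main phase will supply to the economic model, "the health-related quality of life (HRQL) implications of any adverse events experienced with tests", and continues: "The latter will be assessed using the EQ-5D instrument". Section 9.1.2 lists EQ-5D quality of life as a secondary outcome. Section 1.1 makes cost-effectiveness one of three main objectives.

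In Table 2 (section 6.7) the row "EQ-5D Questionnaire" is marked at registration, MP-MRI, combined biopsy and the results visit, and nowhere else. The instrument in Appendix III opens with: "please indicate which statements best describe your own health state today".

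On timing after the biopsy, section 7.2 says below Table 3: "Procedure related AEs would be expected to occur within 7 days of the procedure". Section 6.3 says: "The last study visit should take place within approximately one month of the CPB procedure". It also says what happens there: "At this visit the clinician will discuss the results of all 3 study tests (MP-MRI, TPM biopsy and TRUS biopsy) with the patient".

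The protocol does not say whether the Visit 3 form is completed before or after the biopsy, or whether the Visit 4 form is completed before or after the results are given.

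**The concern.** A questionnaire about the present day records an adverse event only if the man still has it when he completes the form. The protocol expects procedure-related events in the first week, yet schedules no form on days 1 to 7. Acute effects that start and resolve between Visits 3 and 4 therefore leave no trace in the EQ-5D data, and no later analysis can recover them.

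Nothing else in the protocol visibly fills the gap. Section 7.2 provides for no formal toxicity assessment. Table 2 has an SAE form but none dedicated to non-serious events, and section 6.3 only allows side effects to be discussed. Counts of events, if obtained elsewhere, would still carry no quality-of-life value.

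The one form after the biopsy visit coincides with disclosure of all three results. EQ-5D has an anxiety/depression item, so a form completed after disclosure would reflect the diagnosis as well as any remaining procedural effect. At stake is the trial's own estimate of the utility loss from biopsy, which section 10.2.1 says it will provide.

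**Working it through.** **Timeline.** The biopsy follows MP-MRI by at most 3 months (section 6), and Visit 4 follows the biopsy by about 1 month (section 6.3). 3 + 1 = 4 months, which agrees with the follow-up of about 4 months in section 6.9. Of the forms in Table 2, only Visit 4's falls after the biopsy day.

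**Overlap check.** Take onset between day 0 and day 7 (section 7.2) and durations from Table 3, with months converted to days. Earliest end = 0 + shortest duration; latest end = 7 + longest duration. Visit 4 was tried at days 14, 28 and 30. Day 14 is an assumed early visit; the other two reflect the limits of 4 weeks (section 6) and about one month (section 6.3).

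| Event (Table 3) | Duration, days | Earliest end | Latest end | Present at day 14, 28 or 30? |
|---|---|---|---|---|
| Dysuria, TPM | up to 1 | 1 | 7 + 1 = 8 | never |
| Haematuria, TPM | 1–3 | 1 | 7 + 3 = 10 | never |
| Haematuria, TRUS | 2–3 | 2 | 7 + 3 = 10 | never |
| Erectile dysfunction | 42–56 | 42 | 7 + 56 = 63 | always |
| Haematospermia, TRUS | 61–91 | 61 | 7 + 91 = 98 | always |
| Haematospermia, TPM | 91–183 | 91 | 7 + 183 = 190 | always |

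Table 3 gives no duration for dysuria after TRUS, urinary infection, urosepsis or retention, so these cannot be placed in the same way. That much of the infection and retention burden is over by Visit 4 is probable, but it is an assumption.

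**Numbers of men.** Table 3 rates applied to 714 men:
- urosepsis (TRUS, 1–4%): 714 × 0.01 = 7.1 to 714 × 0.04 = 28.6, about 7 to 29;
- urinary infection (TRUS, 1–8%): 7.1 to 714 × 0.08 = 57.1, about 7 to 57;
- retention (TPM, 5%): 714 × 0.05 = 35.7, about 36.

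Dysuria and haematuria are put at almost all men after TPM. None of these events has a scheduled EQ-5D in the week when it is expected.

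**Which day would help.** With onset on the day of biopsy, haematuria is over by day 3 and TPM dysuria by day 1. A single form on day 7 would miss both. A form on day 2 or 3 can catch haematuria that lasts that long, but still misses TPM dysuria that began and ended within the first day, and any event starting later in the week.

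**The case against.** The strongest case against this point has four parts.

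- **Seven days is when events start, not how long they last.** A reader might infer that EQ-5D as scheduled can measure no biopsy harm at all. Table 3 does not support that: erectile dysfunction and haematospermia persist to Visit 4. EQ-5D has no sexual-function item, so they would register only indirectly, through usual activities or anxiety/depression. Visit 4 may also fall earlier than a month, and a Visit 3 form completed after the procedure could pick up some same-day effects. This stands and limits the point to acute, short-lived effects.
- **Mixing with the diagnosis is not shown.** A reader might infer that the Visit 4 values are certainly contaminated, or attach a size to it. The order is simply unstated here, and the separate CRF completion guidelines, which are not shown, may fix it. The protocol gives no utility change for men told they have cancer, and men with reassuring results could move the other way. It is a risk of unknown size and sign.
- **The direction of bias is not shown.** A reader might infer that the schedule understates what MP-MRI saves by sparing men a biopsy. But every man has TPM plus TRUS under general/spinal anaesthesia, whereas section 11.2 describes ordinary TRUS as done under local anaesthetic. A well-timed form would measure the combined procedure and could overstate the loss from the biopsy that MP-MRI would avoid. This stands.
- **Materiality is modest.** The model also draws on secondary sources and elicited opinion, and section 10.2.1 expects test accuracy to be its most important input. On assumed decrements of 0.1 to 0.3 (not from the protocol) lasting a full week, the loss is 0.1 × 7/365 = 0.002 to 0.3 × 7/365 = 0.006 QALY per man. This supports treating the point as minor, but does not explain why the named instrument should miss the period for which it is needed.

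**Conclusion.** The point holds in a limited form. The protocol assigns EQ-5D the task of measuring the quality-of-life effect of test adverse events, then schedules none in days 1 to 7 after the combined biopsy. Dysuria after TPM and haematuria will largely go unrecorded, as will probably much of the effect of infection and retention. Longer-lasting effects may register, indirectly, at Visit 4. Because the order of form and disclosure is not fixed, the Visit 4 values may also carry a diagnosis effect.

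This rests on Table 3's durations, on onset within 7 days, and on a Visit 4 no earlier than about day 14; a visit by day 10 could still catch some late-starting haematuria. The documents support neither a numerical contamination effect nor a direction of bias for or against MP-MRI. The consequence is confined to an economic-model input and a secondary outcome. It is a cheap improvement rather than a flaw in the main analysis.

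**What to change.** Make three changes to Table 2 and the CRF completion guidelines:

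1. Move the Visit 3 EQ-5D to a stated day inside the acute window, early enough for the 1–3 day effects in Table 3, for example day 2 or 3 after the combined biopsy, returned by post or taken by phone. Give the reason for the day, since any single day misses something. Visits 1 and 2 already supply pre-biopsy values.
2. Require the Visit 4 form to be completed before any results are given.
3. State in section 10.2.1 that the decrement estimated is that of the combined TPM and TRUS procedure, not of TRUS biopsy alone.

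The number of forms stays at four, and no visit or procedure is added. The cost is some non-return of the home form, the effort of chasing it, and the loss of a form on the biopsy day. The change must be made before data collection, because values not collected cannot be reconstructed.

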## 8. QUALITY ASSURANCE & CONTROL OF DATA

#### 8.1 Risk assessment

PROMIS is an NCRN-endorsed trial which has undergone independent HTA peer review (expert and consumer representative) and separate reviews by experts on the NIHR HTA committee and the Cancer Group at the MRC CTU.

UCLH and MRC CTU have performed a risk assessment to assess the impact of study participation on the rights and safety of patients, the reliability of the study results and the impact of study results on the site leading the study. This has guided the development of procedures in the study with respect to informed consent, confidentiality and trial monitoring which are recorded in a separate document. It is the view of the Chief Investigator and Trial Management Group that PROMIS is considered to be a low risk study with respect to governance, safety and finance.

#### 8.2 Monitoring at MRC CTU

The MRC CTU will conduct day-to-day central monitoring of the study. Data stored at the MRC CTU will be checked for missing or unusual values and checked for consistency within participants over time. If any problems are identified, a data clarification form will be sent to the centre by post or email for checking and confirmation or correction, as appropriate and returned to the CTU. Any data which are changed should be crossed through with a single line so as not to prevent reading the original and initialled and dated on the site copy of the CRF. MRC CTU will send reminders for any overdue and missing data. It is also our intention to monitor centres for data compliance in terms of data quality and CRF return.

A crucial aspect of the central monitoring will be to check the blinding of the results between assessors/assessments. Central monitoring will be carried out in accordance with the MRC CTU working practices for this trial. Please refer to protocol section 6.8, the PROMIS MRI SOP and the PROMIS Combined Biopsy SOP for more detail on blinding procedures.

#### 8.3 Clinical site monitoring

Participating investigators should agree to allow study-related monitoring, including audits or ethics committee review by providing direct access to source data/documents as required. Patients' consent for this will be obtained as part of the consent process. Details will be provided in the PROMIS Quality Management and Monitoring Plan.

#### 8.4 Data quality control and quality assurance

The data collected will be entered into the study database from the original CRF received from the site. The site will retain a copy of the CRF. If investigator input is required to clarify or correct any missing, ambiguous or inconsistent data, the Data Manager will generate a data query form. The Data Manager will send this form to the study team at the site for completion. When the completed data query form is returned to the MRC CTU, the data on the clinical database will be corrected accordingly.

## 9. STATISTICAL CONSIDERATIONS

In order to recommend that MP-MRI be introduced into the diagnostic pathway for prostate cancer, we require evidence that MP-MRI can do two things.

First, that it correctly identifies a substantial proportion of men who have either no prostate cancer or prostate cancer that is very likely to be clinically insignificant.

Second, that MP-MRI improves the detection rate of clinically significant disease compared to that identified by the current standard, TRUS guided biopsy. If both these test attributes are realised the result will be: fewer biopsies overall but improved detection of clinically important prostate cancer in those men that are likely to benefit from both diagnosis and/or treatment.

PROMIS is adequately powered to measure the precision of MP-MRI specificity to at least 70% (from the lower bound of the 95% confidence interval and assuming MP-MRI has a true specificity of at least 77%) and an increase in sensitivity of MP-MRI by at least 22% (from 48% to 70%) compared to TRUS biopsy.

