The main phase will be extended to approximately 6 centres in total (including the 2 pilot centres), recruiting up to 714 men to have all 3 tests over an additional 2 to 3 years.

The main objectives of the trial are:

- To assess the ability of MP-MRI to identify men who can safely avoid unnecessary biopsy.
- To assess the ability of the MP-MRI based pathway to improve the rate of detection of clinically significant cancer as compared to TRUS biopsy.
- To estimate the cost-effectiveness of an MP-MRI based diagnostic pathway. Using data from the main study and the wider literature, the study will consider the implications of alternative diagnostic strategies for NHS cost and men's quality-adjusted survival duration.

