#### 6.1 Visit 2: MP-MRI

The MP-MRI will be carried out in a 1.5 or 3.0 Tesla scanner with the patient in the supine position. T2, DW and DCE scans will be acquired.

The primary analysis will be based on the local site radiology report. Clinical details including PSA and DRE findings will be known to the reporter. In addition, to determine inter-observer variability and as a quality control measure, double-reporting will be carried out centrally by a number of designated radiologists who will also know clinical details of the case.

Scans will be reported to the MRC CTU on the MRI case report form (CRF) and kept locally by the local site radiologist. Radiologist should refer to the MRI Standard Operating Procedure (SOP). Scans deemed unreadable should be repeated in the same patient whenever possible and appropriate to do so. Cases where MRI scans could not be done/are not readable and are not repeatable should be noted on the MRI CRF that is sent to the MRC CTU (Please see Withdrawal section 6.10 for further information).

An overall whole prostate score will be given (1-5) to indicate the probability of clinically significant cancer:

- Highly likely benign (1).
- Likely benign (2).
- Equivocal (3).
- Likely malignant (4).
- Highly likely malignant (5).

For the primary outcome, an overall score of 3 or more will be used to indicate the possible presence of clinically significant cancer. This reflects the level at which further tests (e.g. biopsy) would be considered if MP-MRI were to be introduced into the diagnostic pathway in the future.

Each reporter will have access to a workstation with mean curve software to be used in the scoring of suspicious lesions (up to a maximum of 6). Images will be reported in sequence: T2  $\rightarrow$  T2+DW  $\rightarrow$  T2+DW+DCE and a separate report produced for each combination of sequences.

For sector analysis, the prostate will be divided into 12 regions of interest (ROI):

- Apex: Right/Left & Anterior/Posterior.
- Mid: Right/Left & Anterior/Posterior.
- Base: Right/Left & Anterior/Posterior.

Radiologists will use the 1-5 score for each ROI.

For each lesion found, the following will be recorded:

- Longest axial diameter.
- Lesion volume.
- Apparent Diffusion Coefficient (ADC).
- DCE-MRI curve shape.

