#### 9.1 Outcome Measures

#### 9.1.1 Primary

There are two primary outcomes in this trial as both are of fundamental importance to decisions regarding the future use of MP-MRI in the diagnostic pathway for the prostate cancer:

- Proportion of men who could safely avoid biopsy as determined by specificity and negative predictive values (NPV)
- 2. Proportion of men correctly identified by MP-MRI to have clinically significant prostate cancer as determined by sensitivity and positive predictive values (PPV)

For the primary outcomes we take DEFINITION ONE (A dominant Gleason pattern  $\geq$  4 and/or a cancer core length  $\geq$  6 mm, see section 2.6) as the criteria for clinically significant prostate cancer as assessed by TPM, the most appropriate reference standard.

Alongside these outcomes, the accuracy of TRUS will also be reported in terms of sensitivity, specificity, NPV, and PPV as listed in the section below. In addition, a head-to-head comparison of the sensitivity of MP-MRI versus TRUS guided biopsy (current standard) will be performed amongst men diagnosed with clinically significant prostate cancer according to TPM.

For the primary outcome, a score of 3 or more on MRI will be used to define a potentially clinically significant cancer (see section 6.1 for details). A dominant Gleason pattern  $\geq$  4 and/or a cancer core length  $\geq$  6 mm will be used for clinically significant cancer (see DEFINITION ONE section 2.6) for the biopsies.

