#### 9.2.3 MP-MRI versus TRUS

We have assumed TRUS detects 48% of clinically significant prostate cancer   and MP-MRI will detect at least 70% (conservative). Using McNemar's test for paired binary observations,  in order to show an absolute increase in the proportion of clinically significant cancers detected of at least 22% (from 48% to 70%) with a power of 90% and a 2-sided alpha of 5%, a total of 107 cases are required. This is equivalent to a total study population of **714** men for DEFINITION ONE, **428** men for DEFINITION TWO.

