#### 9.3.2 Primary analysis of the main study

The primary analysis will be based on all evaluable data, excluding men without all three test results and any data rejected as part of the external MP-MRI QC/QA process (see section 6.6.1).

The sensitivities, specificities and predictive values will be calculated for MP-MRI based on the overall cancer score for MP-MRI and DEFINITION ONE for clinically significant cancer on TPM biopsy. Results will be presented in a 2 by 2 table (as shown below in Table 4) and estimates will be presented together with 95% confidence intervals (CI).

Table 4: 2 by 2 tables to	demonstrate accuracy of MP-MRI	with respect to TPM

		MP-MRI		
		+ve	-ve	Total
TPM	+ve	а	b	a+b
	- ve	С	d	c+d
	Total	a+c	b+d	

**Specificity** = d / (c+d) where, d = number of men testing negative on MP-MRI and negative for clinically significant cancer on TPM, c = number of men testing positive on MP-MRI who do not have clinically significant cancer on TPM.

**Negative Predictive Value (NPV)** = d / (b+d) where, d = number of men testing negative on MP-MRI and negative for clinically significant cancer on TPM, b= number of men testing negative on MP-MRI who have clinically significant cancer on TPM.

**Sensitivity** = a / (a+b) where, a = number of men testing positive on MP-MRI and positive for clinically significant on TPM, b = number of men testing negative for MP-MRI who have clinically significant cancer on TPM.

**Positive Predictive Value (PPV)** = a / (a+c) where, a = number of men testing positive on MP-MRI and positive for clinically significant on TPM, c = number of men testing positive on MP-MRI who do not have clinically significant cancer on TPM.

**Comparison of TRUS guided biopsy and MP-MRI**: McNemar's test will be used to compare the agreement between MP-MRI and TRUS biopsies in the subset of men found to have clinically significant prostate cancer according to DEFINITION ONE. Results will be presented in a 2 by 2 table as shown below in Table 5.

		MP-MRI		
		+ve	-ve	Total
TRUS	+ve	r	S	r+s
	- ve	t	u	t+u
	Total	r+t	s+u	Npairs

Table 5: 2 by 2 table demonstrating the comparison of TRUS guided biopsy and MP-MRI

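### The MP-MRI versus TRUS head-to-head compares cancers flagged with cancers diagnosed, so it cannot by itself show that an MP-MRI pathway improves detection

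*Protocol*

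**What the plan says.** Section 1.1 lists as the second main objective "To assess the ability of the MP-MRI based pathway to improve the rate of detection of clinically significant cancer as compared to TRUS biopsy". Section 9 requires, before MP-MRI can be recommended, evidence "that MP-MRI improves the detection rate of clinically significant disease compared to that identified by the current standard, TRUS guided biopsy", and concludes that meeting both conditions would mean fewer biopsies together with better detection.

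The analysis serving this is in sections 9.1.1, 9.2.3 and 9.3.2. Section 9.1.1 states that "a head-to-head comparison of the sensitivity of MP-MRI versus TRUS guided biopsy (current standard) will be performed" among men with clinically significant cancer on TPM. Section 9.3.2 adds that "McNemar's test will be used to compare the agreement between MP-MRI and TRUS biopsies in the subset of men" with such cancer, laid out in Table 5. The two results compared are:

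- **MP-MRI:** section 6.1 says "an overall score of 3 or more will be used to indicate the possible presence of clinically significant cancer". That score includes the equivocal category and is explained as the level at which further tests such as biopsy would be considered.
- **TRUS:** section 9.1.1 says the dominant Gleason pattern or core-length criterion "will be used for clinically significant cancer (see DEFINITION ONE section 2.6) for the biopsies".

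Section 9.2.3 assumes 48% for TRUS and 70% for MP-MRI, and sizes the test "in order to show an absolute increase in the proportion of clinically significant cancers detected of at least 22" percentage points. Section 9 repeats that 22-point figure as an increase in sensitivity.

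**The concern.** The objective and the section 9 condition concern cancers found by a pathway. The test concerns cancers flagged by its first step. Section 2.2 describes MP-MRI as triage, with the gain in detection coming from biopsies aimed at abnormal areas. Under sections 6.2 and 6.8.1 the surgeon is blind to the MRI and nothing is targeted, and the note to Figure 1 says the proposed pathway is not the one followed in PROMIS. How often a biopsy after a positive MRI would confirm the cancer is thus not directly observed.

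A significant McNemar result would nevertheless naturally be reported as meeting the second objective and the second condition for changing practice. A valid comparison of test sensitivities would then carry a conclusion about detection that it does not test. The 22-point wording adds to this: a reader could take significance as showing a gain of that size.

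**Working it through.** **Inputs.** Section 9.2.3: TRUS 0.48, MP-MRI 0.70, 90% power, two-sided 5%, 107 cases. Section 9.2.1: prevalence 0.15 (DEFINITION ONE). Appendix V Table A1, independence row, in Table 5 notation: both positive r = 0.336; TRUS positive only s = 0.144; MRI positive only t = 0.364; both negative u = 0.156.

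**1. The plan's own figure.** Discordance t + s = 0.508; difference t − s = 0.22.

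n = [1.96·√0.508 + 1.2816·√(0.508 − 0.22²)]² / 0.22² = 106.07, so 107 cases; 107/0.15 = 713.3, so 714 men. The required numbers of cases in the other four rows of Table A1 also reproduce. There is no arithmetic error.

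**2. What 70% means for a pathway.** If a fraction y of MRI-flagged significant cancers is confirmed at biopsy, pathway detection is 0.70·y. It equals TRUS when y = 0.48/0.70 = 0.686. From trial data the same quantity is (r+s)/(r+t), and the ceiling is (r+t)/Npairs. The protocol states no value for y, so the following are assumed values:

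| Assumed y | Pathway detection | Minus TRUS (48%) |
|---|---|---|
| 60% | 42% | −6 points |
| 68.6% | 48% | 0 |
| 80% | 56% | +8 points |
| 90% | 63% | +15 points |
| 100% | 70% | +22 points |

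The full 22 points needs y = 100%. With the section 9.2.2 sensitivities, break-even is 0.48/0.75 = 64% at the assumed value of 75% and 0.48/0.60 = 80% at the lower limit of 60%.

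**3. Power for a pathway contrast at 107 cases.** Assume pathway and TRUS results are independent and let p = 0.70·y. Then b = 0.52·p, c = 0.48·(1 − p), and power = Φ{[(b − c)·√107 − 1.96·√(b + c)] / √[(b + c) − (b − c)²]}.

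- y = 80%: b = 0.2912, c = 0.2112, power about 21%.
- y = 90%: b = 0.3276, c = 0.1776, power about 59%.
- y = 100%: b = 0.364, c = 0.144, power about 90%.

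The stated 90% power therefore applies to the pathway only if every flagged cancer is confirmed.

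**4. What significance shows about 22 points.** McNemar's null hypothesis is a zero difference. With 107 cases and discordance 0.508:

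- Smallest significant difference: 1.96·√(0.508/107) = 0.135.
- 95% CI half-width at an observed 0.22: 1.96·√[(0.508 − 0.0484)/107] = 0.128, so about 9 to 35 points.

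If agreement is closer, as in the first row of Table A1 (discordance 0.23 + 0.01 = 0.24), 107 cases make 1.96·√(0.24/107) = 0.093 significant. A result well short of 22 points can be significant in either case.

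**The case against.** The protocol is often careful. Section 9.1.1 calls the analysis a comparison of sensitivities, sections 6.1 and 9.1.1 treat a score of 3 or more as only possible or potential significant cancer, and section 9 gives the power in terms of sensitivity. As a paired comparison of test sensitivities against TPM the analysis is valid. This stands, and it is why only the claim needs changing. The description of McNemar's test as comparing agreement is loose, but section 9.1.1 makes the intended quantity clear. Stating a sample size as power to show the assumed difference is common shorthand; here, though, the phrase is at least that difference, which the test does not address.

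Three stronger readings are tempting, and the documents do not support them:

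- **That the pathway detects fewer cancers than TRUS.** In the independence row 33.6% are positive on both tests against 48% on TRUS, and the joint figure is below 48% in every row of Table A1. But the share positive on both can never exceed the share positive on one, so any such table gives this. It also describes triage followed by the same untargeted biopsy, whereas section 2.2 proposes biopsies directed by the MRI. The shortfall is only 1 point in the high-agreement row, and section 9.2.4 calls positive dependence more realistic than independence.
- **That the both-positive proportion is all the study can say about a pathway.** Radiologists record where they expect TPM to be positive (section 6.1), TPM cores are individually located (section 6.2), and section 9.3.3 plans matching by region under three rules. The economic model in section 10.2.1 also considers MRI-positive, TRUS-negative results. These could inform a confirmation yield, although the head-to-head does not use them.
- **That a test calling every man positive would succeed.** It would win the head-to-head, which is confined to TPM-positive men, but it would fail the first condition in section 9 and the 70% specificity bound in section 9.2.2.

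**Conclusion.** The point holds as one about the claim. The head-to-head can show that MP-MRI flags more TPM-defined significant cancers than TRUS diagnoses. It cannot show that the pathway detects more, because the confirming biopsy is not part of the study. Improvement is undemonstrated, not disproved.

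On the protocol's 48% and 70%, the pathway advantage runs from none at about 69% confirmation to 22 points at complete confirmation, and is negative below 69%. These break-even figures do not depend on the agreement between MRI and TRUS. The 13.5-point threshold and the 9 to 35 interval do: they assume 107 cases and the independence row. The sample size and the choice of McNemar's test are sound for the narrower question.

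**What to change.** 1. Restate the second objective in section 1.1 and the second condition and conclusion in section 9 along these lines: *MP-MRI (score 3 or more) flags more clinically significant cancers than TRUS biopsy detects.*
2. With the McNemar result, report the paired sensitivity difference with its 95% CI and the break-even confirmation rate (r+s)/(r+t) from Table 5.
3. Show pathway detection over a stated range of assumed confirmation yields, up to the ceiling (r+t)/Npairs. Inform the range where possible by the MRI-TPM regional matching already planned in section 9.3.3, and label the result as modelled.
4. In sections 9 and 9.2.3, replace the wording about an increase of at least 22% with 90% power to detect a true 22-point difference from zero.

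The cost is rewording and a few lines derived from Table 5. No new data, procedures or patients are needed, and the sample size is unchanged. The downside is a more modest claim: a recommendation based on better detection would have to rest on an explicit assumption about biopsy yield.
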